12.3 Stopping Rules

Changes in safety rules are very unlikely and there are no reasons why the study should be stopped.

13. Statistics

13.1 Sample Size

For fMRI comparisons, a minimum N of 20 has been recommended (Thirion et al., 2007). Based on a previous fMRI comparison using whole brain analysis of acute effects of the ATX and MPH on the fMRI brain function in the same working memory task as proposed in this study, we calculated that for a power of 80% we would need an N of 15 subjects for a $p < 0.05$ and N of 20 for a $p < 0.01$ (Cubillo et al., 2013). A sample size of 20 is proposed to account for the fact that the novel contrast of GXR and LDX may potentially have a smaller effect size than the previous comparisons of MPH and ATX. Therefore, to obtain 20 complete datasets 50 patients or more will be screened. This is done to ensure enough participants meet the recruitment criteria and to account for potential dropouts.

13.2 Randomisation

This is a within-patient experimental randomisation design. Each patient gets a single dose of each of the 3 drugs and will be scanned thereafter. The order of drug administration (LDX, GXR, placebo) will be randomised controlling for order effects and the testing will be performed in a double-blind fashion. The supervisor will be responsible for the randomisation and neither the researcher present at scan (i.e. PhD student) nor the parents and patients will know which drug is tested in any given session.

The unblinding will occur at the end of data collection on approval by the Chief Investigator and supervisors. A copy of the blinding will be provided by pharmacy for each study visit to the study team for emergency unblinding. A further copy will be provided to a member of the Department of Neuroimaging unrelated to the study. They can be called at any time to unblind a specific session out of hours if an alternative unblinding option is unavailable.

Unblinding protocol and reporting will be applied according to the local pharmacy procedures.

13.3 Analysis

Analyses of brain activation for the fMRI data will be conducted using SPM (www.fil.ion.ucl.ac.uk/spm) and FSL (www.fsl.fmrib.ox.ac.uk). All performance data will be analysed using SPSS and R. The hypotheses relating activation changes within patients after the acute drug administration will be tested using repeated measures ANOVAs with each of the 3 drug conditions as repeated measures (placebo, GXR, LDX).

Comparison between healthy controls and ADHD patients under placebo and under the two drugs will be conducted by 3 ANOVAs to test for brain abnormalities in ADHD relative to controls at baseline and to test for potential normalisation of the 2 drugs on brain activation.

14. Study Steering Committee

Supervisors will oversee the study.

15. Data Monitoring Committee

As this is an experimental study and not a clinical trial we will not have an external data monitoring committee. The supervisors of the study will form a data monitoring committee and assess the study progress and all other aspects of the study. They will meet once every 6 months.

16. Direct Access to Source Data and Documents

Only the research team and named collaborators will have access to the data.

17. Ethics & Regulatory Approvals

This protocol and related documents will be submitted for review to an NHS Research Ethics Committee (REC).

18. Quality Assurance

Monitoring of this study will be to ensure compliance with Good Clinical Practice and scientific integrity will be managed by the study team.

19. Data Handling

The supervisor will act as custodian for the study data. The following guidelines will be strictly adhered to:

- Patient data will be anonymised.
- All anonymised data will be stored on a password protected computer.
- All study data will be stored in line with the Data Protection Act.
- All study data will be archived in line with Sponsor requirements.
- Audio-recordings will be taken on a password protected encrypted smartphone provided by KCL for the purpose of this study. Only the study team will have access to the smartphone. Participants will provide an opt-in consent to have their recordings taken. Where participants will decide not to have their recordings taken this will not disqualify them from the study. The recordings will be kept on a password protected KCL PC in an anonymised format (as described in the above). Audio-recordings will be destroyed upon completion of the study. Nonetheless, participants will have the option to request to have their information (i.e. audio-recordings and any other material generated by the study) destroyed at any time.

20. Data Management

The data will be behavioural data, cognitive performance data, and fMRI data in electronic format and password protected.

The data to be analysed will be inputted into an SPSS datasheet in a linked-anonymised format.

Data management will follow KCL guidelines.

21. Publication Policy

It is intended that the results of the study will be reported and disseminated at international conferences and in peer-reviewed scientific journals.

22. Insurance/Indemnity

A professional indemnity policy is in place from the sponsor (KCL) for all studies conducted at KCL.

23. Financial Aspects

Funding to conduct the study is provided by Shire Pharmaceuticals Limited.

24. Signatures

Chief Investigator

Date

Print name

Statistician (if applicable)

Date

Print name

25. References

- Chantiluke, C. et al. (2014). *Psychological Medicine* 8, 1-18.
- Christakou, A. et al. (2013). *Molecular Psychiatry* 18, 236-44.
- Clerkin, S.M. et al. (2009). *Biological Psychiatry* 66, 307-312.
- Conners, C.K. et al. (2008). Toronto, Canada: Multi-Health Systems.
- Cubillo, A. et al. (2012). *Cerebral Cortex*, 24(1), 174-185.
- Cubillo, A. et al. (2013). *Psychological Medicine* 44, 633-646.
- DuPaul, G. K. et al. (1998). New York, NY: Guilford Press.
- Fox, H.C. et al. (2012). *Journal of Psychopharmacology* 26, 958-972.
- Fox, H.C. et al. (2015). *Journal of Psychopharmacology* 29, 312-323.
- Hart, H. et al. (2013). *JAMA Psychiatry* 70, 185-198.
- Hill, P. et al. (2001). *Archives of Disease in Childhood*, 84(5), 404-409.
- Jakala, P. (1999). *Neuropsychopharmacology* 20, 460-470.
- Kaufman, J. et al. (1996). Pittsburgh: University of Pittsburgh Press.
- Kim, S. et al. (2012). *Psychopharmacology* 219, 363-375.

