It is generally agreed that for Guanfacine to show clinical effects, it should be administered continuously for approximately 6 weeks. In the case of a single dose study this is a clear limitation. Nonetheless, while behavioural effects might need long term administration to appear, it has been shown in previous fMRI studies that brain function changes will be apparent after a single dose. This is based also on similar observations in studies investigating the related drug Atomoxetine, which is also a noradrenalin agonist. Atomoxetine is also a non-stimulant medication for ADHD that shows behavioural effects after several weeks but we have shown brain function effects after one single dose in ADHD patients (Cubillo et al., 2013; Smith et al., 2013).

ADHD patients will be scanned 4.5 hours after drug administration (where drugs have shown to have maximum plasma concentration). They will be scanned 3 times, one week apart, under each drug condition (LDX, GXR, placebo). Scanning session duration: 60 min.

Healthy controls will be scanned once, under no drug condition, and complete the same protocol as ADHD patients.

Each participant will receive £20 for the pre-assessment visit and £50 for each scanning session to reimburse them for their time (i.e. £170 in total for ADHD patients and £70 for healthy controls). We will also reimburse any travel expenses and can arrange taxis or other travel if required. After each visit participants will receive a token showing the amount that he or she will be paid for the session (i.e. £20 or £50). Payments will be given at the end of the patient's participation in the study, i.e. they will exchange the tokens they collected for money.

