Additionally, the patient will be familiarised with the scanner environment by visiting the "mock scanner" and trained on the tasks he or she will later complete in the actual scanner. If eligible the patient will be invited to come back to the IoPPN to complete the three fMRI scans. Each patient will participate in three testing sessions performed at three separate visits one week apart. Each patient will receive a single typical clinical weight adjusted dose of GXR (0.05mg/kg, being rounded to the closest dose of 1mg, 2mg, or a maximum of 3mg GXR), LDX (30mg if below 30kg, 50mg if above 30kg body weight), and placebo (10mg Vitamin C) in one of the scans, in a randomised order. After approximately 3.5 hours and an hour prior to the scan the participant will complete a battery of the following neurocognitive tasks lasting approximately 40 minutes:

- 1) Go/No-go - 5 min, assessing the participant's ability to inhibit a motor response and selective attention (Rubia et al., 2007)
- 2) Interference inhibition (Simon task) - 5 min, involving a stimulus-response incompatibility effect. The task measures interference inhibition and selective attention. In this task, subjects have to execute a motor response according to iconic information and to inhibit the tendency to make an incorrect response that is triggered by an interfering, and predominant, spatial information (Rubia et al., 2007)
- 3) Continuous performance task - 8 min, measuring target detection, sustained attention, as well as selective attention (Rubia et al., 2007)
- 4) Time discrimination task - 5 min, measuring the participant's ability to discriminate between time intervals that differ by several hundreds of milliseconds (Rubia et al., 2007)
- 5) Vigilance task - 7 min, assessing vigilance on the detection of signals that are difficult to identify (Mackworth, 1948).

Subsequently, patients will be taken to the MRI suite to undergo a brain scan. Patients will be scanned 4.5 hours after drug administration (where drugs have shown to have maximum plasma concentration). The researcher at the scan (i.e. PhD student) will not know which tablet is given on each occasion. This has been designed this way to minimise bias. Medication details will be kept by the supervisor, and will be given to the parents after the three scans have taken place, and to the PhD student to group the data once all the subjects have been scanned.

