In each scanning session, the participants will complete the following tasks that have shown to elicit underactivation in task-relevant regions in ADHD and to be modulated by MPH and ATX:

- 1) Working memory task (N-back task) - 6min, measuring 3 levels of working memory difficulty and will also assess the default mode network decrease with progressively increasing working memory (Cubillo et al., 2013, Chantiluke et al., 2014)
- 2) Tracking stop task - 9min, measuring motor response inhibition and error monitoring (Rubia et al., 2005, 2011; Cubillo et al., 2013)
- 3) Parametric sustained attention task - 12min, investigating the effects of increasing load on sustained attention on brain activation (Christakou et al., 2013, Murphy et al., 2015)
- 4) Resting state fMRI - 8min, measuring intrinsic connectivity networks associated with ADHD (default mode network, cognitive control network, dorsal and ventral attention,

saliency, and motor networks).

Total scanning time for each session will be approximately 60 minutes. The duration of testing for each subject will be 3 weeks.

Additionally, a group of 20 healthy age-matched controls will be recruited. Healthy controls will have no diagnosis of ADHD or other major psychiatric conditions, they will be psychoactive-medication free, have no history of substance abuse and no neurological deficits, learning disability, reading, speech, or language disorder. Healthy controls will be assessed using the following measures during their first visit at the IoPPN:

- 1) Edinburgh Handedness Inventory (Oldfield, 1971)
- 2) IQ (WASI-II) (Wechsler et al., 1999)
- 3) Social Communication Questionnaire (Rutter et al., 2001)
- 4) The Conners-Third Edition: Parent Rating Scales, Short Form [Conner 3- P(S)] to assess ADHD and other disorders (Conners, 2008)

Additionally, the participant will be familiarised with the scanner environment by visiting the "mock scanner" and trained on the tasks he or she will later complete in the actual scanner. If eligible the participant will be invited to come back to the IoPPN for a testing session that will involve the same cognitive and fMRI tasks as conducted with ADHD patients. The duration of testing for each healthy control will be one week or less.

12. Assessment of Safety

12.1 Specification, Timing and Recording of Safety Parameters.

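### The within-patient ANOVA in section 13.3 has no session term; adding one is a cheap precision gain whose size depends on session drift relative to the within-patient SD

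*Combined protocol and SAP*

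**What the plan says.** Section 13.3 tests activation changes within patients by "repeated measures ANOVAs with each of the 3 drug conditions as repeated measures (placebo, GXR, LDX"). No session, period or sequence term appears there or elsewhere. For performance data the section names software but no model.

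Section 13.2 deals with order at allocation: "The order of drug administration (LDX, GXR, placebo) will be randomised controlling for order effects". It names no scheme and gives no counts per sequence.

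Section 8.1 sets the schedule: "They will be scanned 3 times, one week apart, under each drug condition (LDX, GXR, placebo"). Section 11 has the scanner tasks repeated at every visit ("In each scanning session, the participants will complete the following tasks"). It also has patients "trained on the tasks he or she will later complete in the actual scanner" at the pre-assessment, before the first scan.

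Section 13.1 gives the power basis from an earlier drug comparison: "for a power of 80% we would need an N of 15 subjects" at p<0.05, and 20 at p<0.01. It adds that "the novel contrast of GXR and LDX may potentially have a smaller effect size than the previous comparisons of MPH and ATX".

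**The concern.** Activation or performance may shift from the first scan to the third, for example through practice or growing familiarity with the scanner. The plan treats order effects as worth controlling but does not carry that control into the model. Any shift common to patients then has nowhere to go except the residual or the drug contrasts.

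- With near-balanced orders it inflates the residual, and the drug test becomes conservative.
- With simple randomisation it enters the realised drug contrasts by chance, with mean zero.

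What is at stake is the precision of the within-patient analysis of the primary imaging endpoints. This is separate from carry-over. Section 8.2 derives washouts of 4.6 and 2.4 days, both shorter than the 7-day interval, so no carry-over term is considered here.

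**Working it through.** **The plan's own figures.** Section 13.1 states no effect size. Let dz be the paired difference divided by the SD of the within-patient difference. Solving a two-sided paired t test for 80% power gives dz = 0.78 from N=15 at p<0.05 and dz = 0.84 from N=20 at p<0.01. Carrying the N=15 effect to p<0.01 gives N = 21 to 22 with a three-level repeated measures ANOVA. The stated pair of 15 and 20 is therefore consistent to within about 2 patients.

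**Inputs.** N = 20 complete datasets and three sessions come from sections 13.1 and 8.1. Two inputs are assumptions: dz, back-solved at 0.78 with 0.6 and 0.39 as smaller effects, and drift, given as the mean at sessions 1, 2, 3 in within-patient SD. Errors are independent with SD 1, so the drug effect is dz × √2 (0.78 × 1.414 = 1.10 SD). There is one scalar outcome with pooled error.

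**Degrees of freedom.** There are 20 × 3 = 60 observations. Patient plus drug leaves 60 − 20 − 2 = 38 error df. Adding session leaves 36.

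**Closed form, balanced orders.** The drug-only residual mean square is 1 + 20 × SS/38, where SS is the sum of squared deviations of the session means.

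| Drift (SD) | SS | Residual mean square | 20 patients worth about |
|---|---|---|---|
| 0, 0.3, 0.5 | 0.127 | 1.07 | 18.8 |
| 0, 0.5, 0.8 | 0.327 | 1.17 | 17.1 |
| 0, 1.0, 1.5 | 1.167 | 1.61 | 12.4 |

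**Simulated power (%) for a pairwise contrast, drug-only v drug plus session.** Near-balanced means 4/4/3/3/3/3 over the six sequences, because 20 is not a multiple of 6.

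| Drift (SD) | Near-balanced, dz 0.78, p<0.05 | Near-balanced, dz 0.78, p<0.01 | Near-balanced, dz 0.6, p<0.05 | Simple, dz 0.78, p<0.05 |
|---|---|---|---|---|
| none | 92 v 92 | 77 v 76 | 74 v 74 | 92 v 91 |
| 0, 0.3, 0.5 | 91 v 92 | 75 v 77 | 73 v 75 | 91 v 91 |
| 0, 0.5, 0.8 | 89 v 92 | 70 v 76 | 68 v 74 | 88 v 91 |
| 0, 1.0, 1.5 | 81 v 92 | 52 v 77 | 55 v 74 | 77 v 90 |

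With simple randomisation and no drift, the term loses about 2 points at p<0.05 and about 3 at p<0.01. It breaks even near 0, 0.3, 0.5 SD.

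**Validity.** Mean bias of the drug-only contrast was within 0.004 SD in every cell. Over the four drift rows, its type I error at a nominal 5% was 5.2, 4.3, 3.7 and 1.7 with near-balanced orders, and 4.9 to 5.1 with simple randomisation.

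**Scale of drift.** Now set linear drift, from session 1 to session 3, equal to the drug effect (p<0.05, pairwise). At dz 0.78 the near-balanced gain is about 5 points (86.6 v 92.0). At dz 0.39 it is about 3 points (36.4 v 39.2), and nil under simple randomisation (37.8 v 37.8).

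**The case against.** The strongest reply is that nothing here threatens the analysis. Order is randomised, no drift is documented, and task training before the first scan makes large drift less likely. Even at 0, 1.0, 1.5 SD, drug-only power at dz 0.78 and p<0.05 is 81% with near-balanced orders or 77% with simple randomisation, close to the 80% used in section 13.1. All of that stands, and it sets the severity.

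A second reply is that section 13.2 says only that order is randomised. If that means simple randomisation, the session term costs a little when drift is small. This stands too, and is why the order scheme belongs in the fix. The reference list ends with a 1949 entry that the text never cites. A reader might take it as a sign of a balanced crossover design, but the documents do not say so.

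Two stronger readings are tempting. A reader might infer that omitting session biases the drug comparison or produces false positives; the randomised order and the type I error figures do not support that. A reader might also infer that the term matters once drift matches the drug effect, whatever the size of that effect. It does not: drift relative to the within-patient SD drives the loss. At the same absolute drift, the loss at p<0.05 is larger at dz 0.6 than at dz 0.78. But drift merely equal to a small effect (dz 0.39) gains only about 0 to 3 points.

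**Conclusion.** The missing session term is certain from the text. It is a precision matter and not a validity flaw. Whether it costs anything in this study is unknown, because both the drift and the effect size are assumptions. At dz 0.78 with near-balanced orders, the loss is negligible up to about 0, 0.3, 0.5 SD, modest at 0, 0.5, 0.8 SD, and substantial only at 0, 1.0, 1.5 SD, especially at p<0.01. Section 13.3 sets no alpha, so both levels are shown.

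The figures assume a drift common to all patients and drugs; patient-specific drift would stay in the residual. They describe one scalar outcome and do not transfer directly to whole-brain inference. The session term does not help the three patient-control ANOVAs, where controls are tested once. Severity: minor, a cheap improvement.

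**What to change.** Make two linked wording changes before unblinding, which section 13.2 places at the end of data collection.

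1. In section 13.3, state that the within-patient model contains patient, drug and session (1, 2, 3). Use a flexible-factorial or equivalent model for imaging, and the same terms for performance data.
2. In section 13.2, state that orders are spread as evenly as possible over the six sequences, if allocation is not already balanced. With 20 patients that is 4/4/3/3/3/3.

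No extra patients or scans are needed. The price is 2 of 38 error degrees of freedom, which is under 1 point of power with near-balanced orders and no drift. If orders were simply randomised and there is no drift, the price is the 2 to 3 points shown above; the second change avoids most of it.

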10.4 Withdrawal of Subjects

There is little evidence for side or adverse effects of the single dose LDX and GXR, hence withdrawal due to adverse effects is not expected. Nevertheless, potential adverse effects have been listed in the participant information sheet which will be provided to participants and their parents for their information. Participation will be discontinued if

- *the participant decides they no longer wish to continue*
- *recommended by the investigator*

Should a patient decide to withdraw from the study, the reason for withdrawal will be recorded as detailed as possible.

Participants who wish to withdraw from the study will be asked to confirm whether they are still willing to provide the study specific data at visits that were completed.

10.5 Expected Duration of Study.

1st May 2018 – 31st December 2020

Provided a timely reception of ethical approval we will begin recruitment in May and expect to begin testing the first participant by June 2018. We predict that we will be able to test one participant a month, depending on participant and scanner availability. We aim to finalise data collection by 31st December 2020 latest. Following that, we will begin data analysis, preparation of publications, and the PhD student will begin thesis write up.

11. Study Procedures

The following procedure will be followed in this study:

We will recruit 20 young people aged between 8 and 20 years with a current diagnosis of ADHD, who have never taken medication for ADHD (medication-naïve) or who have not been on ADHD medication for at least 3 months. All participants will have no history of substance abuse and no neurological deficits, learning disability, reading, speech, or language disorder, no other major clinical psychiatric disorder other than ADHD and autism, and no contraindications for LDX or GXR. These patients will be identified within SLAM and other clinics and will have already received a diagnosis of ADHD from a clinician or will be on a community waiting list awaiting clinical ADHD assessment. The family will be given a letter inviting the patient to participate as well as an information sheet.

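### The within-patient repeated measures ANOVA, in its usual form, gives no weight to patients with an incomplete three-scan set; a mixed model on all usable sessions would be modestly more precise

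*Combined protocol and SAP*

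**What the plan says.** Section 13.3 (Analysis) tests the within-patient activation hypotheses by "repeated measures ANOVAs with each of the 3 drug conditions as repeated measures", namely placebo, GXR and LDX. It then plans three ANOVAs that compare controls with patients under placebo and under each drug. It gives no analysis set, no rule for a missed or unusable scan, and no mixed model.

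Section 13.1 (Sample Size) counts complete sets: "to obtain 20 complete datasets 50 patients or more will be screened", partly "to account for potential dropouts". It gives neither a dropout rate nor a replacement rule.

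Section 10.4 (Withdrawal of Subjects) has withdrawing patients asked whether they are "still willing to provide the study specific data at visits that were completed". Section 12.1 also foresees that some patients may not tolerate repeated scanning, and lets a participant end a session at any time.

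**The concern.** The protocol takes steps to keep data from patients who do not finish, but its main within-patient test by default cannot use them. A patient scanned under placebo and one drug carries direct information on that contrast; a classical three-condition ANOVA gives that patient zero weight.

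Two things are at stake. One is precision: usable scans already obtained from children and adolescents are set aside. The other is who is analysed: only patients who completed every condition. Section 12.2 lists drowsiness, dizziness, headache and fatigue as possible side effects, and any of these could plausibly end or spoil a scan. Completeness is also a matter for each task separately, because every session has three task runs and a resting run (section 7.1.1).

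**Working it through.** **The plan's own figure.** Section 13.1 states N = 15 at p < 0.05 and N = 20 at p < 0.01 for 80% power. It gives no effect size, so neither can be rebuilt. As a consistency check, the effect that gives N = 15 at 0.05 needs 22 by repeated measures F, or 22–23 by two-sided paired t, at 0.01, against the stated 20. Nothing below depends on these figures.

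**Inputs.** From the documents: three conditions per patient and a target of 20 complete sets. Assumed, because not given: compound symmetry with within-patient correlation ρ = 0.5 (range 0.3–0.7), and the number or rate of lost sessions.

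**Weight of an incomplete patient.** Take the information on a pairwise drug contrast from one complete patient, 1/(1−ρ), as 1. Averaged over which sessions are missing, generalised least squares gives:

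- two scans: w₂ = (2+ρ)/[3(1+ρ)]. At ρ = 0.5 this is 2.5/4.5 = 0.556. It is 0.590 at ρ = 0.3 and 0.529 at ρ = 0.7.
- one scan: w₁ = (1−ρ)/3. At ρ = 0.5 this is 0.167.

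The complete-set ANOVA sets both to 0.

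**Case A: 20 complete sets are reached, with m further incomplete patients.** Variance ratio, complete-set to all-data = (20 + m·w)/20.

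| m | two-scan patients | one-scan patients |
|---|---|---|
| 2 | (20 + 1.11)/20 = 1.056 | (20 + 0.33)/20 = 1.017 |
| 4 | (20 + 2.22)/20 = 1.111 | (20 + 0.67)/20 = 1.033 |
| 6 | (20 + 3.33)/20 = 1.167 | (20 + 1.00)/20 = 1.050 |

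The closed form assumes missing sessions spread evenly over conditions. Random missing patterns, with period in the model, bring the two-scan column to about 5%, 11% and 16%. For m = 4 over ρ = 0.3–0.7, the closed form gives 1 + 0.2 × 0.590 = 1.118 to 1 + 0.2 × 0.529 = 1.106. On the standard error scale, √1.111 = 1.054, or about 5%.

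**Case B: 20 start and nobody is replaced; each session is lost independently with probability q.** Expected complete sets are 20(1−q)³. The ratio of expected information at ρ = 0.5 is 1 + (5/3)r + (1/2)r², with r = q/(1−q). The last column is the mean ratio over simulated patterns. It is slightly higher because it averages over the random number of complete sets.

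| q | complete sets of 20 | closed form | simulated |
|---|---|---|---|
| 5% | 17.1 | 1.09 | 1.09 |
| 10% | 14.6 | 1.19 | 1.20 |
| 15% | 12.3 | 1.31 | 1.33 |
| 20% | 10.2 | 1.45 | 1.48 |

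Over ρ = 0.3–0.7 the simulated 10% figure stays at about 1.19–1.22. As an example in power: take the paired effect of 0.84 SD that gives 80% at N = 20 and two-sided 0.01. If 4 of 20 lose one scan, power is 66% on the 16 complete sets, against 74–75% using all scans.

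**Bias.** With sessions lost at 5%, 30% and 10% by condition, and otherwise at random, simulated completers recovered true contrasts of 0.5 and 1.0 as 0.50 and 1.00. Bias appears when loss is correlated with the patient's own drug effect. With an assumed correlation of 0.3–0.5 and 10–20% of patients lost, a true effect of 0.84 becomes about 0.66–0.78 among completers, or moves upward by the same amount if the correlation has the other sign.

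**The case against.** The strongest reply is that section 13.1 recruits until 20 sets are complete. The planned precision is then kept, and what is forgone is information beyond the plan. This stands: it makes Case A the main reading and Case B a fallback. Case B cannot be dismissed, because no replacement rule is given and capacity is tight. Section 10.5 predicts one participant a month. June 2018 to December 2020 is about 31 months, against 40 planned participants if both groups share that rate.

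A second reply is that the loss the documents foresee is mainly withdrawal, perhaps after the first scan, rather than scattered single sessions. This also stands. One-scan patients add little (2–5% in variance), and no document supports a rate of 15–20% per session.

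Three stronger readings are tempting, and the documents do not support them:

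- A reader might infer that the data kept under section 10.4 are never analysed. Each of the three control comparisons uses one patient condition, so a patient with one or two scans can enter it.
- A reader might infer that the plan excludes incomplete patients by rule. Section 13.3 does not say so, and the 20 complete datasets are a recruitment target, not a defined analysis set. An ANOVA fitted by least squares with a patient factor would use two-scan patients.
- A reader might infer that results are biased whenever one drug causes more lost scans. Loss that depends only on the drug taken does not bias completers' within-patient contrasts.

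**Conclusion.** The point holds as a modest and avoidable loss of precision in the within-patient test, together with unstated handling of incomplete sets. If 20 complete sets are reached, the variance of a drug contrast is about 5%, 11% or 16% larger than necessary with 2, 4 or 6 extra two-scan patients, and 2–5% larger with one-scan patients. If 20 start without replacement, it is about 9–48% larger for assumed losses of 5–20% per session. All these figures rest on an assumed correlation of 0.5 and assumed loss, since the documents give neither.

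Recruiting to 20 complete sets does not remove selection on having completed every session. Whether that biases the contrasts depends on a link between loss and individual response that the documents do not quantify. A mixed model helps only where that link runs through observed data; it does not cure loss that depends on the unseen response.

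**What to change.** In section 13.3:

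- For task performance and extracted activation, replace the repeated measures ANOVA with a linear mixed model fitted by REML to all usable sessions: patient random, condition and period fixed, small-sample degrees of freedom. The period term is needed because incomplete sets unbalance condition against visit.
- For whole-brain maps, use a group model with patient, condition and period factors that accepts unequal sessions per patient. With patient as a fixed factor, one-scan patients contribute nothing and a two-scan patient counts for about half (w₂ tends to 0.5 as ρ tends to 1), so the gain in Case A is about 5%, 10% or 15%.
- Keep the target of 20 complete sets, and give the complete-set ANOVA as a sensitivity analysis.
- State for each task the analysis set and what makes a scan unusable, and state whether incomplete patients are replaced.
- Report missing or unusable scans by condition and visit.

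The cost is a change of wording and slightly more analysis work, mostly for the whole-brain model. R is already named for the performance data, and no new data are needed.
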